#### 4.11.5 Exploratory Efficacy Analysis

Exploratory analyses will be done using a similar model to the primary endoscopic NPS endpoint analysis. Endpoints will include:

- Change from baseline at Week 24 in FEV1 for subjects with asthma
- Change from baseline at Week 16 in endoscopic NPS
- Change from baseline at Week 16 in Average daily NCS
- Change from baseline at Week 24 in European quality of life scale (EQ 5D-5L)

Weekly mean of daily nasal congestion score will be calculated as sum of non-missing daily nasal congestion score divided by number of days with non-missing daily nasal congestion score using analysis window (Table ).

Proportion of subjects with minimal clinically important difference  $\geq 8.9$  in SNOT-22 at Week 24 will be calculated with the corresponding 95% CI by treatment group. Clopper-Pearson interval will be used to calculate the exact confidence interval for binomial proportion. The difference between each CBP-201 group and placebo group and the corresponding 95% CI will be calculated as well. Cochran–Mantel–Haenszel (CMH) test stratified by presence of comorbid asthma will be performed and odds ratio will be provided with 95% confidence interval.

The sample SAS code for CMH test:

```
proc freq data=data order=data;
  table trt01pn*snot*cmabl / relrisk cmh;
run;
```

Healthcare resource utilization at each visit up to Week 24 will be summarized using descriptive statistics by treatment and overall, as described in 4.13.4.

By-subject listings of each exploratory efficacy endpoint will also be provided.

### 4.12 Safety Evaluation

#### 4.12.1 Extent of Exposure

Duration of treatment (see 4.2 for definition), cumulative amount of study drug administered during treatment period, and number of injection interruption will be summarized on Safety Set by treatment and overall. By-subject listing of extent of exposure will also be provided.

#### 4.12.2 Adverse Events

Adverse events will be coded using the Medical Dictionary for Regulatory Activities (MedDRA) Version 24.0. Severity and causality of AE will be evaluated by the investigator. Severity of AE will be graded according to the Common Terminology Criteria for Adverse Events (CTCAE), version 5.0. Incomplete start and end date of the AE will be imputed as described in **Error! Reference source not found.**

Subjects with multiple incidents of events for a given preferred term (PT) and system organ class (SOC) will be counted only once. Similarly, if a subject experiences multiple incident of events for a given PT and SOC, the worst severity will be used in the summaries presenting severity, and the worst causality to study drug will be used in the summaries presenting causality, respectively.

Any missing severity will be queried for completion. If the severity is still missing in the final data and the outcome of AE is death, then it will be deemed as Grade 5, and if the life-threatening is marked, then it will be deemed as Grade 4. Otherwise, the severity still missing in the final data will be deemed as Grade 3.

Any missing causality will also be queried for completion, and any events that still have missing causality in the final data will be deemed as 'Related'.

The imputed severity and relationship will be used in table summary, but the original value will be maintained as missing in the by-subject listing.

Adverse event summaries will be sorted in terms of decreasing frequency for SOC, and PT within SOC, in the overall group, and then alphabetically for SOC, and PT within SOC if there are any ties in frequency.

An overall summary of AEs will include the number and percentage of subjects in the following categories:

- Any AEs
- AEs by maximum severity
- Any AEs related to study drug
- Any AEs related to study procedure
- Any AEs occurring more than 5% of subjects in overall
- Any serious AEs
- Any AEs leading to death
- Any AEs leading to study drug discontinuation
- Any AEs leading to study drug interruption
- Any TEAEs
- TEAEs by maximum severity
- Any TEAEs related to study drug
- Any TEAEs related to study procedure
- Any TEAEs occurring more than 5% of subjects in overall
- Any serious TEAEs

- Any TEAEs leading to death
- Any TEAEs leading to study drug discontinuation
- Any TEAEs leading to study drug interruption

Summaries of following AEs including the number and percentage of subjects will also be provided:

- AEs by SOC and PT
- Serious AEs by SOC and PT
- TEAEs by SOC and PT
- TEAEs by SOC and PT for Subjects with Rescue Medications
- TEAEs by decreasing frequency of PT
- TEAEs by SOC, PT, and maximum severity
- TEAEs of grade 3 or higher by SOC and PT
- TEAEs related to study drug by SOC and PT
- TEAEs related to study procedure by SOC and PT
- Any TEAEs occurring more than 5% of subjects in overall
- Serious TEAEs by SOC and PT
- TEAEs leading to death by SOC and PT
- TEAEs leading to study drug discontinuation by SOC and PT
- TEAEs leading to study drug interruption by SOC and PT

By-subject listings of corresponding adverse events summary will also be provided.

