**REVISION HISTORY**

Version No.	Effective Date	Summary of Change(s)
0.1	15-Jun-2021	New document
0.2	14-Jul-2021	Updated per Connect team review
1.0	30-Jul-2021	Updated per CRM especially adding sensitivity analysis for use of rescue medication and statistical analysis for proportion of patients with minimal clinically important difference $\geq 8.9$ in SNOT-22 at Week 24. Also subgroup analyses were added and minor language was updated in rescue medication per client request
1.1	18-Jan-2022	Updated per protocol amendment v3.0 and internal/Connect team review
1.2	25-Jan-2022	Updated per Connect team review
1.3	19-May-22	Updated to include change due early termination of the study.
1.4	15-Jun-22	Updated section 4.3.1 and section 4.15

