#### 4.12.3 Adverse Event of Special Interest

The TEAEs of special interests are defined as:

- Conjunctivitis
- Keratitis
- Anaphylaxis
- Parasitic and opportunistic infections
- Pregnancy
- Symptomatic overdose
- Injection site reactions lasting longer than 24 hours
- AST/ALT elevated > 5X ULN

The TEAEs of special interests will be summarized using frequencies and percentages by SOC and PT. Further analysis on AESI will also be summarized including the risk difference, its 95% confidence interval, and p-value using CMH test stratified by presence of comorbid asthma if there are at least 4 subjects in any treatment arm. The risk difference will be computed as each CBP-201 treatment group versus placebo. The confidence intervals and p-values will not be adjusted for

multiplicity so should be considered accordingly. By-subject listings will also be provided for all AESIS.

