#### **4.15 Changes in the Conduct of the Study or Planned Analysis**

Enrollment of Sponsor's Phase 2 trial evaluating CBP-201 in chronic rhinosinusitis with nasal polyps, which commenced in June 2021, has faced challenges due to the macroenvironment -- namely ongoing impact of COVID and the current Russia-Ukraine conflict throughout [Eastern] Europe.

Therefore, the Sponsor has made the decision to terminate this trial early, and the planned analyses have been changed to focus on safety assessments.

For the efficacy endpoints, only descriptive summary statistics will be provided for the co-primary efficacy assessments. No formal hypotheses will be tested due to the small sample size. No sensitivity or subgroup analyses will be performed. All other efficacy assessments will be listed except percentage of maxillary sinus volume occupied by disease on CT and Lund-Mackay Computed Tomography scores.

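### After early termination the SAP makes safety the focus but keeps crude adverse event percentages; if follow-up was cut short these can understate risk, and supplementary exposure-adjusted rates would be a cheap improvement

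*SAP*

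**What the plan says.** SAP 4.15 records that "the Sponsor has made the decision to terminate this trial early, and the planned analyses have been changed to focus on safety assessments". The Revision History dates that change to version 1.3 of 19 May 2022 ("Updated to include change due early termination of the study"). Section 4.15 cuts efficacy back to descriptive summaries and listings. It changes nothing in the safety methods of 4.12.

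Those methods count subjects. In 4.12.2, "An overall summary of AEs will include the number and percentage of subjects in the following categories", and "Subjects with multiple incidents of events for a given preferred term (PT) and system organ class (SOC) will be counted only once". For adverse events of special interest (AESIs), 4.12.3 adds: "Further analysis on AESI will also be summarized including the risk difference, its 95% confidence interval, and p-value using CMH test", applied when at least 4 subjects in any arm have the event. The sentence in 4.15 that withdraws hypothesis testing stands in the paragraph on efficacy endpoints, so it does not clearly remove this p-value.

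Related provisions are:
- SAP 4.12.1 summarises duration of treatment and cumulative drug by arm. SAP 4.2 defines that duration as last dose minus first dose plus one day.
- SAP 4.5.1 tabulates discontinuations by arm with reasons, and by-subject listings are planned.
- Protocol 8.3 collects adverse events from consent to Visit 17 (Week 32) or an Early Termination Visit, whichever is first.
- SAP 4.2 limits treatment-emergent events (TEAEs) to the treatment period. Protocol 9.6 runs them from first dose to the end of follow-up.

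Neither document plans an incidence rate per person-time, a time-to-event analysis of adverse events, or a summary of how long patients were under observation.

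**The concern.** When nearly everyone is followed for the same 32 weeks, the percentage of subjects with an event estimates a 32-week risk. When a trial stops early and follow-up is truncated, the denominator mixes patients watched for a few weeks with patients watched to the end. The percentage then no longer refers to any stated period. It sits below the full-period risk, and a true difference between arms shrinks with it. Safety is now the main output of this trial, so its tables should show how much observation lies behind each percentage. The existing exposure summary does not do this. It measures dosing time, omits observation after the last dose, and is not linked to any event count.

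**Working it through.** The documents give no adverse event rate, no number randomised and no follow-up figures, so there is no stated figure to reproduce. The event risks, entry patterns and arm sizes below are assumptions.

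**1. Is truncation plausible?** The trial is one "which commenced in June 2021"; SAP version 1.3 is dated 19 May 2022. Week 32 is Day 225, 224 days after first dose. Counting back 224 days from 19 May 2022 gives 7 October 2021. A patient first dosed after that date could not have reached Week 32 by the date of version 1.3. Follow-up is therefore unequal if patients were cut off near then. The documents do not say that they were.

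**2. Size of the understatement.** Assume a constant hazard with 20% risk by Week 24:
- λ = −ln(0.8)/24 = 0.00930 per week.
- Week-32 risk = 1 − exp(−32λ) = 25.7%.
- Let T be weeks from first dose to cut-off, uniform on 0 to E, and let follow-up be F = min(32, T). The expected crude percentage is the mean of 1 − exp(−λF).
- E = 48 (about June 2021 to May 2022): mean F = 32 − 32²/96 = 21.3 weeks. Crude = [32 − 0.2573/λ + 16 × 0.2573]/48 = (4.32 + 4.12)/48 = 17.6%.
- E = 24 (all entry in the last 24 weeks): mean F = 12 weeks. Crude = 1 − 0.2/(24λ) = 10.4%.

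**3. Sensitivity to the assumptions.**
- *Eight further weeks observed after stopping drug (protocol 3.4), same hazard.* F = min(32, T + 8). The integral of 1 − exp(−λt) from 8 to 32 is 4.03. Crude = (4.03 + 24 × 0.2573)/48 = 21.3% for E = 48, and 4.03/24 = 16.8% for E = 24, against 25.7%.
- *TEAE window of SAP 4.2 (treatment period only).* The benchmark is the 20% Week-24 risk and F = min(24, T). Crude = (2.49 + 24 × 0.20)/48 = 15.2% for E = 48, and 10.4% for E = 24.
- *Early events.* With follow-up uniform over 2 to 32 weeks and all events in the first 8 weeks, a 20% risk shows as 18.6% and a 40% risk as 37.4%, about 93% of the true value. Under a constant hazard and the same follow-up, 20% shows as 11.0% and 40% as 23.0%.

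**4. Risk differences.** From the last figures, a true 20-point difference (20% versus 40% at Week 32) appears as 23.0 − 11.0 = 12.0 points.

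**5. Bias between arms.** Simulated 1:1 comparisons with no drug effect and the same follow-up distribution in both arms (40,000 runs) gave mean crude differences of 0.04 to 0.07 points at 10, 20 and 49 per arm, which is zero within simulation error.

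Chance imbalance can be sized from step 2 with E = 48. The standard deviation (SD) of 1 − exp(−λF) across patients is 0.0837, against a total event variance of 0.1758 × 0.8242 = 0.1449.

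| Assumed patients per arm | SD of crude difference from follow-up imbalance, 0.0837 × √(2/n) | Total SD of crude difference, √(2 × 0.1449/n) |
|---|---|---|
| 10 | 3.7 points | 17.0 points |
| 15 | 3.1 points | 13.9 points |
| 20 | 2.6 points | 12.0 points |

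The share of variance is 0.0837²/0.1449, about 5%.

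Differential discontinuation is different in kind. With follow-up uniform over 2 to 32 weeks, if one arm also loses 30% of its patients at Week 12, its crude percentage falls from 23.0% to 20.7% (40% risk) or from 11.0% to 9.8% (20% risk), with no difference in hazard.

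**The case against.** The strongest reply is that truncation is assumed. SAP 4.15 gives enrolment difficulty as the reason for stopping and does not say that enrolled patients were cut off. Protocol 3.4 provides 8 weeks of follow-up after early discontinuation of drug. A reader might infer that follow-up did differ widely; the documents do not support stating that as fact. This stands, and it makes the understatement conditional. It also shows a gap, because a plan revised for termination should say what happened to ongoing patients.

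A reader might also infer that the arm comparison is biased because arms were watched for different lengths of time. Under stratified 1:1:1 randomisation with a common stop, it is not. The crude difference is centred on zero when there is no effect, and chance follow-up imbalance is about 5% of its variance. Only differential discontinuation can bias it, and SAP 4.5.1 at least tabulates discontinuation by arm.

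Third, the constant hazard is a choice. Protocol 8.6 reports that conjunctivitis with the related drug typically began in Weeks 4 to 8 in atopic dermatitis. For early events the percentage loses little, while a person-time rate itself varies with length of follow-up. This stands, and is why rates should supplement the percentages.

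Finally, subject counts and percentages are conventional in a small descriptive Phase 2 report, and exposure, disposition and listings give partial information. That lowers the priority. It does not supply the missing observation time.

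**Conclusion.** The point holds as a cheap improvement, not as a demonstrated error in the safety results. SAP 4.15 makes safety the focus, while 4.12.2 and 4.12.3 keep measures suited to a fixed course and no measure of observation time is planned.

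If patients were cut off at termination, the percentages can fall well short of full-period risk: 17.6% or 10.4% in place of 25.7% under a constant hazard and uniform entry over 48 or 24 weeks. The shortfall is smaller if 8 further weeks were observed (21.3% or 16.8%), and small for events in the first 8 weeks. If all patients completed Week 32, it disappears. Risk differences shrink in the same way. The comparison of arms is not systematically biased by a common stop; the remaining risks are differential discontinuation and, to a small degree, chance imbalance in small arms. Every figure here rests on assumed entry, hazard and arm size.

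**What to change.** 1. Reconcile the TEAE window between SAP 4.2 (treatment period) and protocol 9.6 (first dose to end of follow-up). This comes first: counting person-time to the end of follow-up under the SAP definition would add up to 8 weeks of denominator in which no event can count.
2. In SAP 4.15, state whether patients ongoing at termination completed follow-up. In the adverse event table headers, give total patient-years and median time under adverse event observation by arm.
3. In SAP 4.12.2 and 4.12.3, keep the number and percentage and add, as a supplement, subjects with a first event per 100 patient-years at risk with 95% CI by arm, for any TEAE, serious TEAEs, TEAEs leading to study drug discontinuation, and each AESI. Time at risk runs from first dose to the earliest of first event, end of the reconciled TEAE window, and end of observation. For AESIs that meet the existing 4-subject threshold, add the rate difference versus placebo.

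The cost is SAP wording and a few columns, because the dates are already collected. The downside is that a rate assumes a roughly constant hazard and will be imprecise with few patients, so the rates should sit beside the percentages and not replace them.

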#### 4.12.3 Adverse Event of Special Interest

The TEAEs of special interests are defined as:

- Conjunctivitis
- Keratitis
- Anaphylaxis
- Parasitic and opportunistic infections
- Pregnancy
- Symptomatic overdose
- Injection site reactions lasting longer than 24 hours
- AST/ALT elevated > 5X ULN

The TEAEs of special interests will be summarized using frequencies and percentages by SOC and PT. Further analysis on AESI will also be summarized including the risk difference, its 95% confidence interval, and p-value using CMH test stratified by presence of comorbid asthma if there are at least 4 subjects in any treatment arm. The risk difference will be computed as each CBP-201 treatment group versus placebo. The confidence intervals and p-values will not be adjusted for

multiplicity so should be considered accordingly. By-subject listings will also be provided for all AESIS.

#### 4.12.4 Clinical Laboratory Evaluation

All laboratory values will be reported and summarized using standard international (SI) units ([Appendix D – Laboratory SI U](#)). CTCAE v5.0 will be used for the laboratory toxicity grade ([Appendix E: CTCAE V5.0 Toxicity Grading for Laboratory Parameters](#)).

The following central laboratory tests will be summarized:

- Hematology: red blood cell count, hemoglobin level, hematocrit level, white blood cell count with differential, and platelet count
- Serum Chemistry: blood urea nitrogen (BUN), creatinine, uric acid, total bilirubin, sodium, potassium, calcium, chloride, bicarbonate, alkaline phosphatase (ALP), aspartate aminotransferase (AST), alanine aminotransferase (ALT), lactate dehydrogenase (LDH), gamma-glutamyltransferase (GGT), creatine phosphokinase (CPK), albumin, total protein, total cholesterol, triglycerides, C-reactive protein (CRP), and glucose
- Urinalysis: pH, protein, glucose, ketones, bilirubin, blood (hemoglobin), urobilinogen, nitrites, leukocytes, and specific gravity; microscopic analysis if abnormal

Continuous test results for each parameter and changes from baseline will be summarized at each visit by treatment and overall using descriptive statistics. Categorical test results for each parameter will be summarized at each visit by treatment and overall using frequencies and percentages. Shift of laboratory toxicity grade from baseline to each post-baseline visit will be summarized by treatment and overall. By-subject listings of laboratory parameters will also be provided.

Laboratory values will be listed by subject and study time point including changes from baseline, where available. All values outside the clinical reference ranges will be flagged in the data listings. The abnormal values will be flagged with 'L' for values below the lower limit of the clinical reference range and 'H' for values above the upper limit of the clinical reference range and included in the listings.

#### 4.12.5 Vital Signs

Descriptive summaries of actual values and changes from baseline at each visit will be summarized for temperature, systolic blood pressure, diastolic blood pressure, heart rate, and respiratory rate by treatment and overall. Baseline of vital signs is defined as pre-dose at Baseline visit. By-subject listing of vital sign parameters will also be provided.

#### 4.12.6 Electrocardiograms

Descriptive summaries of actual values and changes from baseline at each visit will be summarized for the electrocardiogram parameters by treatment and overall. A separate summary of abnormal findings will be provided using frequencies and percentages. By-subject listing of electrocardiogram parameters will also be provided.

#### 4.12.7 Physical Examinations

A complete or brief physical examinations will be conducted at Screening; Baseline; Weeks 1, 2, 4, 6, 8, 10, 12, 14, 16, 18, 20, 22, 24, 28 during treatment period; Week 28 and End of Study visit during follow-up period.

A complete physical examination will be conducted at Screening and End of Study visit, and includes:

- General appearance
- Head, eyes, ears, nose, and throat (HEENT)
- Neck
- Thyroid
- Skin
- Cardiovascular system
- Respiratory system
- Lymph nodes
- Musculoskeletal system
- Abdomen
- Fundoscopy (if available)
- Nervous system
- Extremities

A brief physical examination will be in all other visits and includes:

- General appearance
- Eyeball
- Lungs
- Lymph nodes

Abnormal findings of physical examinations will be summarized at each visit using frequencies and percentages by treatment and overall. By-subject listing of all physical examination parameters will also be provided.

#### **4.12.8 Data and Safety Monitoring Board (DSMB)**

An independent Data Safety Monitoring Board (DSMB) will be set up periodically to review and evaluate all tolerability, descriptive primary efficacy data, and safety data for subject safety, study conduct and progress, and to make recommendations to the sponsor concerning the continuation, modification, or termination of the trial. The DSMB will be comprised of relevant clinical experts, drug safety and benefit-risk assessment experts, clinical trial methodology experts, and an independent DSMB biostatistician. These members will not be directly involved in the conduct of the study. Each meeting will be consisted of open and closed session. Unblinded information will be only reviewed during the closed session to maintain blinding and to prevent potential bias. The meeting minutes containing unblinded information will be marked as “Confidential” and distributed to the members of the DSMB only.

A separate DSMB Charter document will outline further details about the DSMB responsibilities and authorities, schedule of data review, define the board process, communications, meeting format, data access, and the lists of the reports.

## 4.13 Other Analyses

### 4.13.1 Pharmacokinetics

Whole blood for plasma CBP-201 concentrations will be collected, and additional sampling will be obtained after the last treatment dose to characterize the return to Baseline, as noted in the schedule of assessment. The individual and treatment group steady-state trough pharmacokinetic (PK) profile will be calculated for PK analysis.

The details of PK analysis will be provided in a separate PK analysis plan.

### 4.13.2 Pharmacodynamics

Pharmacodynamic (PD) blood samples for biomarkers of inflammation include peripheral eosinophil counts, Eotaxin-3, eosinophil cationic protein (ECP), total immunoglobulin E (IgE), thymus and activation-regulated chemokine (TARC), and periostin. Blood eosinophil count will be measured as part of hematology test and included in hematology summary. CRP will be determined as part of the serum chemistry and included in serum chemistry summary. Absolute analysis value and change from baseline of peripheral eosinophil counts, Eotaxin-3, eosinophil cationic protein (ECP), total immunoglobulin E (IgE), thymus and activation-regulated chemokine (TARC), and periostin to each visit will be summarized by treatment using descriptive statistics on PK Set. By-subject listing will also be provided.

